8.10 Efficacy Follow-up Visit (Telephone Contact)

The Efficacy Follow-up Visit is conducted as a telephone contact at Week 4 and applies to patients who withdraw from the study during the treatment period and prior to Week 3, except for those who withdraw their consent.

If the Withdrawal Visit takes place during the treatment period and prior to Week 3, then the eDiary assessments should continue on a daily basis until the Efficacy Follow-up Visit (Week 4).

At the Efficacy Follow-up Visit, a compliance check of the eDiary will be conducted. The eDiary closeout will take place at the Efficacy Follow-up Visit. Patients will not be required to complete the PRO assessments. Details will be provided in a separate *eDiary and PRO training material*. Adverse events, concomitant medication (prescription and non-prescription), and non-pharmacological interventions will be collected.

If the Withdrawal Visit takes place at Week 4, an Efficacy Follow-up (telephone contact) Visit at Week 4 is not required and the eDiary closeout must take place at the Withdrawal Visit (see section 8.9).

8.11 End-of-study Definition

The end of the study for an individual patient is defined as the last protocol-specified contact with that patient. The overall end of the study is defined as the last protocol-specified contact with the last patient ongoing in the study.

9 Assessments

9.1 Screening and Baseline Procedures and Assessments

9.1.1 Demographics and Baseline Characteristics

Prior to enrolling a patient in the study, the investigator must ascertain that the patient meets the selection criteria.

The following assessments will be performed after the *Informed Consent Form* has been signed:

- Demographics (age, sex, race)
- Migraine history (including diagnosis of migraine and MOH) *

- Relevant history (social, medical, psychiatric, neurological)
- Prior migraine treatment history for review and documentation of previous preventive medication use including treatment failures (see below for definition) ** within the 10 years prior to the Screening Visit (see chapter 12 for adequate required documentation)
- Other recent medication (including acute migraine medications)
- Substance use (alcohol, tobacco, caffeine, marijuana consumption) ***
- Height without shoes
- Blood sample for screening (e.g., β -hCG [beta-human chorionic gonadotropin], FSH, hepatitis B surface antigen [HBsAg], hepatitis B surface antibody [anti-HBs], hepatitis B core antibody [anti-HBc], and anti-HCV) and other clinical safety laboratory tests (as listed in Panel 5)
- Urine sample for screening (drug and alcohol screen) and other clinical safety laboratory tests (as listed in Panel 5)
- Signs and symptoms present at the Screening and/or Baseline Visits (before IMP administration)
- **CCI** [REDACTED]
- Vital signs (including blood pressure, pulse, respiratory rate, and body temperature), weight without shoes, ECGs
- Physical and neurological examinations must be performed prior to the infusion.
- C-SSRS to systematically assess suicidal ideation and behaviour of patients for safety (see section 9.5.7)

*Patients with a concurrent diagnosis of MOH are allowed to be included in the study. At the Screening Visit, the investigator must confirm whether or not the patient has a concurrent diagnosis of MOH.

**Treatment failure could have been due to inadequate efficacy (that is, no clinically meaningful improvement at the locally recommended dose for at least 3 months) and/or safety/tolerability reasons (that is, discontinuation due to adverse events) and/or contraindications (that is, ineligibility due to medical reasons).

*** Substance use <3 months prior to screening will be collected at the Screening Visit. Substance use during the screening period will be collected at the Baseline Visit. Substance use throughout the study (including any changes in substance use) will be collected at select visits until the Safety Follow-up/Withdrawal Visit.

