Recent medication (prescription and non-prescription), herbal remedies, non-pharmacological interventions, vitamin and mineral supplements	√							
Height	√							
Blood sampling for serology (HBsAg, anti-HBs, anti-HBc, and anti-HCV)	√							
Blood sampling for other screening (e.g., β-hCG, FSH)	√							
Urine drug screen and alcohol screen	√							
Inclusion/exclusion criteria	√	√						
Signs and symptoms present at Screening and Baseline (before IMP administration) (recorded on an Adverse Event Form)	√	√						
CCI		√ ^j						
Randomization		√						
Efficacy Assessments								
eDiary daily recording ^{f,g}	√	√ ^j	√	√	√	√ ^{e,k}	√ ^k	√ ^k

Visit Name	Screening	Baseline + IMP		Primary Outcome		Safety Follow-up	Withdrawal ^f	Efficacy Follow-up (telephone contact) ^e
Visit Number	1 SCR	2 BL	3	4 PO	5	6 SFU	WD	EFU
Type of Visit ^x	Clinic	Clinic	Clinic /Tele visit / Home	Clinic /Tele visit / Home	Clinic /Tele visit / Home	Clinic	Clinic /Tele visit / Home	Tele phone
Day/End of Week ^a	-4	0	2	4	8	12		4
Visit Window ^b (days relative to nominal visit)	-2		±2	±2	±2	±5		±2
eDiary compliance check ^{f,h}		✓	✓	✓	✓	✓ ^c	✓	✓
CCI		█	█	█	█	█	█	
	█	█		█	█	█	█	
		█	█	█	█	█	█	
		█		█	█	█	█	
		█		█	█	█	█	
		█		█	█	█	█	
		█		█	█	█	█	
		█		█	█	█	█	
		█	█	█	█	█	█	
		█		█	█	█	█	
		█		█	█	█	█	
		█		█	█	█	█	
		█		█	█	█	█	
		█		█	█	█	█	
		█		█	█	█	█	
		█		█	█	█	█	
		█		█	█	█	█	
		█		█	█	█	█	
		█		█	█	█	█	
Pharmacokinetic Assessments								
Blood sampling for CCI quantification		✓ ^l	✓	✓	✓	✓	✓	
Exploratory Pharmacodynamic Assessments								
Blood sampling for CCI		✓ ^l	✓	✓	✓	✓	✓	
Blood sampling for CCI		✓ ^m		✓				
Blood sampling for CCI		✓ ^m		✓				
Safety Assessments								
Adverse events	✓	✓ ^{m,n,o}	✓	✓	✓	✓	✓	✓
Blood and urine sampling for clinical safety laboratory tests	✓	✓ ^m	✓	✓	✓	✓	✓	
Blood sampling for ADA including NAb		✓ ^m	✓	✓	✓	✓ ^p	✓	
Vital signs (including body temperature), weight, ECGs	✓	✓ ^{m,n}	✓	✓	✓	✓	✓	
Examinations (physical) ^q	✓	✓ ^m		✓		✓	✓	
Examinations (neurological) ^q	✓	✓ ^m				✓	✓	
C-SSRS ^r	✓	✓ ^m	✓	✓	✓	✓	✓	

Visit Name	Screening	Baseline + IMP		Primary Outcome		Safety Follow-up	Withdrawal ^f	Efficacy Follow-up (telephone contact) ^e
Visit Number	1 SCR	2 BL	3	4 PO	5	6 SFU	WD	EFU
Type of Visit ^x	Clinic	Clinic	Clinic /Tele visit/ Home	Clinic /Tele visit/ Home	Clinic /Tele visit/ Home	Clinic	Clinic /Tele visit/ Home	Tele phone
Day/End of Week ^a	-4	0	2	4	8	12		4
Visit Window ^b (days relative to nominal visit)	-2		±2	±2	±2	±5		±2

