9.5 Safety Assessments

9.5.1 Adverse Events

The patients will be asked a non-leading question (for example, “how do you feel?”, “how have you felt since your last visit?”) at each visit, starting at the Screening Visit. Adverse events (including worsening of concurrent disorders, new disorders, and pregnancies) either observed by the investigator or reported spontaneously by the patient will be recorded, and the investigator will assess the seriousness and the intensity of each adverse event and its relationship to the IMP. Results from relevant tests and examinations, such as clinical safety laboratory tests, vital signs, and ECGs, or their corresponding conditions, will also be recorded as adverse events if considered by the investigator to be clinically significant.

See chapter 10 for further information on adverse events.

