16.9 Safety Analyses

16.9.1 Analysis of Adverse Events

Adverse events will be classified according to the time of onset of the adverse event:

- *pre-treatment adverse event* – an adverse event that starts on or after the date the patient signed the *Informed Consent Form* and prior to the date of first dose of IMP
- *treatment-emergent adverse event* – an adverse event that starts or increases in intensity on or after the date of first dose of IMP

Adverse events, sorted by system organ class and preferred term, will be summarized by treatment group.

Allocation of TEAEs to Study Periods

TEAEs may be allocated to study periods (these will be defined in the SAP).

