13.1.3 Classification of Adverse Events

Adverse events will be classified according to the time of onset of the adverse event:

- *pre-treatment adverse event* – an adverse event that starts on or after the date the participant signed the *Informed Consent Form* and prior to the date and time of the dose of IMP.
- *treatment-emergent adverse event (TEAE)* – an adverse event that starts during or after administration of the dose of IMP, or a pre-treatment adverse event that increases in intensity or becomes serious during or after administration of the dose of IMP.

For handling of adverse events with incomplete start dates to facilitate this classification, see section 22.3.5. Note that adverse events with incomplete start dates will be classified as treatment-emergent simply if the imputed start date is on or after the date of IMP infusion, since the start time of the adverse event will not be imputed, unless the investigator in such a case has assessed that the causality to IMP is *not related - prior to IMP*.

An adverse event is considered causally related to the use of the IMP when the causality assessment by the investigator is *probable* or *possible*. If the causality assessment is missing, the adverse event is considered possibly causally related.

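### SAP 13.1.3 limits treatment-emergent worsening to events that began after consent, while Protocol 16.9.1 does not, so some worsening of older Adverse Event Form entries is left out of the TEAE summaries

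*Protocol*

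**What the plan says.** Protocol section 9.1.1 names "Signs and symptoms present at the Screening and/or Baseline Visits (before IMP administration" as an item to be assessed but does not say where it is recorded. Panel 2 does: "Signs and symptoms present at Screening and Baseline (before IMP administration) (recorded on an Adverse Event Form".

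SAP section 13.1.3 defines a pre-treatment adverse event as "an adverse event that starts on or after the date the participant signed the *Informed Consent Form* and prior to the date and time" at which the IMP is given. Its TEAE definition has two limbs. The first is onset during or after administration. The second is "or a pre-treatment adverse event that increases in intensity or becomes serious during or after administration of the dose of IMP".

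Protocol section 16.9.1 defines a TEAE as "an adverse event that starts or increases in intensity on or after the date of first dose of IMP".

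Two recording rules bear on how worsening reaches the database:

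- Protocol section 9.5.1 counts worsening as an event in its own right: "Adverse events (including worsening of concurrent disorders, new disorders, and pregnancies" are to be recorded. Section 7 requires the same when a concomitant medication dose is raised because a concurrent disorder has worsened.
- Protocol section 10.3 sends a change in intensity of an existing adverse event to the AE Intensity Log. SAP section 22.4.2 stores such changes as several rows and counts them as one event.

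**The concern.** The second limb of the SAP definition takes in only events that already qualify as pre-treatment adverse events, and that term starts at consent. The Adverse Event Form can hold older entries, because it is also where symptoms found at Screening are written down. Such an entry falls in neither SAP class, and the SAP rule gives it no way into the TEAE class by worsening. The protocol definition does.

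Safety and tolerability is a stated objective, and the arms are compared mainly on the TEAE summaries. Worsening of an existing symptom after an infusion is a tolerability signal. Whether it is counted should not depend on how a site entered it, and the SAP should not count it differently from the protocol without saying so.

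**Working it through.** No arithmetic applies, and the plan gives no figure to reproduce. The check applies both definitions to each combination of onset and recording route, for a symptom that worsens after dosing (cases 1 to 3) or whose start date is incomplete (case 4).

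| Case | Onset and recording | Protocol 16.9.1 | SAP 13.1.3 |
|---|---|---|---|
| 1 | Onset between consent and dose; worsens after dose | TEAE | TEAE (second limb) |
| 2 | Onset before consent; worsening entered as a separate adverse event (Protocol 9.5.1, section 7) | TEAE | TEAE (first limb: the new record starts after dosing) |
| 3 | Onset before consent; already on the form; worsening entered only as an intensity change (Protocol 10.3, SAP 22.4.2) | TEAE | Neither pre-treatment nor treatment-emergent |
| 4 | Onset before consent; start date wholly missing, or only the year known and equal to the dosing year | No imputation rule given | Imputed to the dosing date (SAP 22.3.5), so TEAE unless the investigator judged it unrelated because it preceded the IMP |

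Only case 3 separates the two documents. The steps that lead to it are:

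1. Panel 2 puts symptoms present at Screening on the form. A symptom found at that visit can predate consent.
2. If its intensity later changes, section 10.3 calls for a log entry and does not call for a new event. The recorded start date therefore stays before consent.
3. With that start date the record fails the SAP's pre-treatment definition. It therefore cannot use the worsening limb, and it fails the onset limb as well.
4. Under Protocol 16.9.1 the increase in intensity after dosing is enough.

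Cases 3 and 4 together give an odd result. An event whose start date is wholly missing is normally counted as a TEAE with no evidence of worsening, while an event known to predate consent and known to have worsened is not counted.

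A case 3 record would be absent from the TEAE summaries in SAP 13.1.5 and, where relevant, from the treatment-emergent SAE summary in 13.1.7 and the TEAE summaries in 13.1.8 and 13.1.9. It would remain visible elsewhere. SAP 13.1.4 lists all adverse events with a TEAE flag, 13.1.1 includes each intensity of an event that changes, and 13.1.7 lists all SAEs. The overview in 13.1.4 counts SAEs without a treatment-emergent qualifier.

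**The case against.** The strongest reply is that the protocol already has a route for this. Section 9.5.1 makes worsening of a concurrent disorder an adverse event, and SAP section 8 defines a concurrent disorder as one ongoing at the Screening Visit. A record opened that way starts after dosing and is a TEAE under both documents. This stands. A reader might infer that all worsening of older symptoms disappears from the TEAE tables, and the documents do not support that. What remains is that nothing says this route replaces section 10.3 for a symptom already on the form, so either entry is consistent with the protocol.

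The protocol also uses consent as a boundary: sections 10.1.1 and 16.9.1 describe pre-treatment events as starting after, or on or after, consent. That is so, but the worsening part of its TEAE definition is not tied to that boundary. The SAP's is.

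Two further inferences are tempting but should not be drawn.

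- It is not shown that many form entries predate consent. Consent may be signed before the Screening Visit (sections 4.2 and 8.2), Baseline symptoms follow a screening period of 28 to 30 days, and older conditions are also collected as relevant history.
- The rules in SAP 22.3.5 for start years before the dosing year do not show that pre-consent records are expected. SAP 22.3.4 uses the same algorithm for medication start dates, and consent in December with dosing in January would need those rules too.

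The SAP is also broader than the protocol in one respect, since it adds events that become serious. Finally, much of SAP section 21 on changes from the protocol is redacted. None of the headings legible in the contents list (21.1 to 21.5) concerns adverse event classification, but 21.6 to 21.8 cannot be read, so an explanation there cannot be excluded.

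**Conclusion.** The concern holds in a limited form. For an Adverse Event Form entry with onset before consent, whose post-dose worsening is logged only as a change in intensity, the protocol definition gives a TEAE and the SAP definition read literally does not. The record is lost from the TEAE summaries but not from the listings.

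The size is unknown. The documents give neither the share of patients with such an entry, nor the chance that it worsens, nor how often sites would log the change rather than open a new event. A percentage of the 230 patients would rest entirely on assumed inputs.

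The conclusion assumes that the derivation follows the wording of SAP 13.1.3 and that some form entries predate consent. It does not touch the primary efficacy analysis. It is a conflict between two definitions of a main safety outcome, and it is worth removing because that is easy to do.

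**What to change.** In the worsening limb of SAP 13.1.3, replace the reference to a pre-treatment adverse event with: any adverse event with onset before the dose of IMP, including Adverse Event Form entries with onset before consent. Leave the rest of the limb (increase in intensity, becoming serious, and timing relative to administration) as it is. The worsening rule then covers the same onsets as Protocol 16.9.1 and keeps the SAP's seriousness criterion. Entries that do not worsen stay outside the TEAE class.

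If the narrower rule is intended, state it and the reason for it among the changes from the protocol in SAP section 21. An instruction to enter such worsening always as a new adverse event would also close the gap, but it would have to be reconciled with Protocol 10.3 and would depend on site practice.

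The cost is one clause in the SAP and one line of derivation code. The downside is that TEAE counts may rise slightly.

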9.1.2 Diagnostic Assessments

The ICHD-3 guidelines¹ section 1.1 Migraine without Aura, or 1.2 Migraine with Aura, or 1.3 Chronic Migraine are the diagnostic criteria to be used when assessing patient eligibility (see Panel 4).

Panel 4 ICHD-3 Guidelines for Migraine¹

1.1 Migraine without Aura	1.2 Migraine with Aura

A. At least five attacks fulfilling criteria B–D
 
B. Headache attacks lasting 4–72 hours (when untreated or unsuccessfully treated)
 
C. Headache has at least two of the following four characteristics:
 
 1. unilateral location 2. pulsating quality 3. moderate or severe pain intensity 4. aggravation by or causing avoidance of routine physical activity (e.g., walking or climbing stairs) 
D. During headache at least one of the following:
 
 1. nausea and/or vomiting 2. photophobia and phonophobia 
E. Not better accounted for by another ICHD-3 diagnosis.
	
A. At least two attacks fulfilling criteria B and C
 
B. One or more of the following fully reversible aura symptoms:
 
 1. visual 2. sensory 3. speech and/or language 4. motor 5. brainstem 6. retinal 
C. At least three of the following six characteristics:
 
 1. at least one aura symptom spreads gradually over ≥ 5 minutes 2. two or more aura symptoms occur in succession 3. each individual aura symptom lasts 5–60 minutes 4. at least one aura symptom is unilateral 5. at least one aura symptom is positive 6. the aura is accompanied, or followed within 60 minutes, by headache 
D. Not better accounted for by another ICHD-3 diagnosis.

1.3 Chronic Migraine
 
A. Headache (migraine-like or tension-type-like) on ≥ 15 days/month for >3 months, and fulfilling criteria B and C
 
B. Occurring in a patient who has had at least five attacks fulfilling criteria B–D for 1.1 Migraine without Aura and/or criteria B and C for 1.2 Migraine with Aura
 
C. On ≥ 8 days/month for >3 months, fulfilling any of the following:
 
 1. criteria C and D for 1.1 Migraine without Aura 2. criteria B and C for 1.2 Migraine with Aura 3. believed by the patient to be migraine at onset and relieved by a triptan or ergot derivative 
D. Not better accounted for by another ICHD-3 diagnosis.
	

ICHD-3 = International Classification of Headache Disorders Third Edition.

9.1.3 Classifications for Eligibility

Fulfilment of criteria for migraine, according to the eligibility criteria in this protocol, will be confirmed via prospectively collected information in the eDiary during the screening period, i.e., migraine occurring on CCI and headache occurring on ≤ 26 days. Prior to randomisation, the investigator will review the data in the *eDiary Eligibility Report* to determine if eligibility criteria are fulfilled.

Definition of a Migraine Day: The definition is based on the IHS guidelines^{17,18} for controlled studies of preventive treatment of CM and EM in adults. A migraine day is defined as a day with a headache that:

- lasts ≥ 4 hours and meets ICHD-3 criteria C and D for migraine without aura (1.1),
- or lasts ≥ 30 minutes and where the patient had an aura with the headache (migraine with aura*),
- or lasts ≥ 30 minutes and meets two of the three ICHD-3 criteria B (without the condition on 72 hours), C and D for migraine without aura (1.1) (probable migraine**),
- or a day with a headache that is successfully treated with a triptan, ergotamine, or other migraine-specific acute medication (for this purpose the master medication list will be classified into “migraine-specific” and “non migraine-specific” medication).***

Data on characteristics of a headache will be collected in the eDiary on a daily basis for each headache day, and for each headache day it will be determined whether it qualifies as a migraine day.

If a headache lasts ≥ 72 hours, the days will still be counted as *headache days* or *migraine days* as aligned with the IHS guidelines.¹⁷

A day where the symptoms are not recorded for an ongoing headache (missed data entry) will be classified as a headache day.

Further details on the definitions:

CCI

Definition of a Headache Day: A Headache Day is defined as a day with a headache that lasts ≥ 30 minutes or that meets the definition of a Migraine Day.

CCI

CCI

Definition of a Compliant Day: A Compliant Day is defined as any day where the following information is available:

- headache diary is completed: a headache event is reported to take place and patient records daily symptoms, or
- headache diary is completed: confirming patient does not have any new headache to report.

9.1.4 Drug and Alcohol Screen

A urine drug and alcohol screen will be performed. If the patient has tested positive for drugs of abuse (cocaine, amphetamines, phencyclidine, propoxyphene), then the patient should be excluded. Note: Positive results for opiates, cannabinoids, and barbiturates should not be a reason for exclusion.

9.2 Efficacy Assessments

Efficacy assessments include the eDiary to record daily headache data, CCI

Patients will record eDiary headache data on a daily basis from the time of screening until the Safety Follow-up Visit or Efficacy Follow-up/Withdrawal Visit.

CCI

PROs which are scheduled in alignment with a visit can be completed on the day or within 3 days prior to the scheduled visit date. On the Baseline Visit day, patients must complete the PROs at the visit date and prior to infusion (see [Panel 2](#)).

9.2.1 Clinical Outcome Assessments

9.2.1.1 Use of Clinical Outcome Assessment Tools

The clinical outcome assessment (COA) tools include the eDiary and PROs, and guidance will be given on how to complete them to the patients by designated site staff (see section [9.2.1.12](#)). Detailed instructions will be provided to the site in a separate *eDiary* and *PRO site information guide*. Site staff will be given access to review the eDiary data.

CCI [REDACTED]

The COA tools will be administered in the local language. Only linguistically validated translated COAs provided by Lundbeck will be used in this study.

The following COA tools will be used for efficacy assessments:

- eDiary – to assess daily headache and migraine variables, i.e., the number of hours with headache, presence of associated symptoms, and use of acute migraine medications start and stop dates, and headache severity.

- CCI [REDACTED]

9.2.1.2 eDiary

Patients will complete a daily headache eDiary, from the Screening Visit until the Safety Follow-up Visit or Efficacy Follow-up/Withdrawal Visit, that consists of applications and reports that will be used to derive the migraine and headache endpoints. The eDiary will be distributed to each patient at the Screening Visit after patient training on eDiary use. The eDiary data from the 28 days following the Screening Visit will be used to determine eligibility criteria, baseline migraine and headache values, and eDiary compliance. See section 9.1.3 for definition of a Migraine Day, Headache Day and Compliant Day during the Screening Period. Ongoing evaluation of eDiary compliance will be performed by the study site based on eDiary reports. At the Screening Visit, the patient must be assisted with the provisioning of the eDiary and must be trained in eDiary use and compliance requirements by designated site staff. The patient will also receive training on the questions which will be asked in the eDiary. Access to training material will be available throughout the study. Patients will be instructed to complete the eDiary on a daily basis, from the Screening Visit until the Safety Follow-up Visit or Efficacy Follow-up/Withdrawal Visit. During the Safety Follow-up Visit or Efficacy Follow-up/Withdrawal Visit, the eDiary closeout must be performed. Details will be provided in a separate *eDiary site information guide*.

The content of the headache diary is developed on key symptoms and characteristics as mentioned in the definition of migraine (see section 9.1.2). For each day, the patient will record if they experienced any headaches. For each experienced headache, the start and stop

date and time will be collected. The patient will record further daily information regarding headache characteristics (for instance, headache severity, additional symptoms) and intake of headache/migraine acute medication. Headache items will be assessed with a yes/no response; and severity will be rated as mild, moderate, or severe. Additional details regarding the questions that patients will answer can be found in the *eDiary training material*.

The Screening Visit will correspond to the day of eDiary distribution and will start the 28-day eDiary screening period. Any patient found to be ineligible for the study during the screening period will not be randomised. An *eDiary Eligibility Report* will be used to review headache eDiary data (including baseline headache and migraine days and eDiary compliance) during the 28-day screening period and for the eligibility assessment of:

- migraine occurring on CCI and headache occurring on ≤ 26 days.
- compliance by entry of headache data for at least 24 of the 28 days following the Screening Visit.

Prior to randomisation, the investigator will review the data in the *eDiary Eligibility Report* to determine if eligibility criteria are fulfilled.

On the Baseline Visit (dosing) day, patients must complete the eDiary recording of headaches that ended prior to infusion (for example, for headaches which are ongoing or not yet recorded in the eDiary).

On each day during the study until the Safety Follow-up Visit or Efficacy Follow-up/Withdrawal Visit, the patient will be asked to record eDiary data for the day.

Site staff will be given access to review the eDiary data. Compliance data (based on eDiary reporting) will be made available throughout the study to site staff for review on a regular basis. At each visit, a compliance check of the eDiary will be conducted. Additionally, ongoing evaluation of eDiary compliance will be performed by the site and more frequent contact with patients may be needed in case of non-compliance. All follow-up with patients regarding eDiary compliance should be documented in the source records.

CCI

[REDACTED]

[REDACTED]

[REDACTED]

CCI [Redacted]

[Redacted]

[Redacted]

[Redacted]

[Redacted]

[Redacted]

[Redacted]

[Redacted]

